1.0 Research Design

1.1 Purpose/Specific Aims

The primary purpose of this study is to compare the effectiveness of a usual care (UC) vs. targeted generic print (TP) vs. tailored telephone counseling and navigation intervention (TCN) on cancer genetic risk assessment (CGRA) uptake at 6 months for hereditary breast and ovarian cancer (HBOC). Secondary purposes are: 1) to compare the effectiveness of a TP vs. a TCN intervention vs. UC on CGRA uptake at 12 months, after removal of key access barriers; 2) to compare uptake of genetic testing for HBOC across the three study arms at 6 and 12 months; 3) to compare cognitive (beliefs, attitudes, and knowledge) and affective (distress, stress, fear) intermediate endpoints among women in the three study arms and explore potential underlying theoretical mediating and moderating mechanisms that will further specify and elucidate significant intervention effects; and 4) to perform an economic evaluation alongside this randomized controlled trial to estimate the cost effectiveness of the two interventions compared to each other and usual care, for uptake of CGRA services from the societal and payer perspectives.

The New Jersey State Cancer Registry (NJSCR) will collaborate with investigators from the state cancer registries of Colorado and New Mexico ([name] = overall Principal Investigator) to identify women recently diagnosed with high-risk breast and ovarian cancer. The NJSCR will (a) recruit and consent New Jersey patients who are eligible to participate in the study, and (b) securely send contact and cancer-related information to the overall PI for women who consent so that they can be enrolled onto study by the overall PI. This application is for case ascertainment using the NJCSR.

A. Objectives

AIM 1: Compare the effectiveness of a TP vs. a TCN intervention vs. UC on CGRA uptake 6 months (primary outcome) after the intervention and at 12 months, after removal of key access barriers.

AIM 2: Compare uptake of genetic testing for HBOC across the three study arms at 6 and 12 months.

AIM 3: Compare cognitive (beliefs, attitudes, and knowledge) and affective (distress, stress, fear) intermediate endpoints among women in the three study arms and explore potential underlying theoretical mediating and moderating mechanisms that will further specify and elucidate significant intervention effects.

AIM 4: Perform an economic evaluation alongside this randomized controlled trial to estimate the cost effectiveness of the two interventions compared to each other and usual care, for uptake of CGRA services from the societal and payer perspectives. This aim provides information about the value of the interventions from both societal and payer perspectives, given a cost per effect measure and the uncertainty surrounding the estimate.

[figure not shown]
B. Hypotheses / Research Question(s)

Primary Hypothesis: Compared to UC, CGRA (genetic counseling) uptake at 6 months (primary outcome) will be highest among women participating in the TCN arm followed by women participating in the TP arm.

1.2 Research Significance (Briefly describe the following in 500 words or less):

HBOC Cancer Risks and Genetic Risk Prediction. Identification of individuals at increased risk of HBOC is crucial for cancer survivors and their families to benefit from biomedical advances. In 2015, approximately 254,000 new cases of ovarian cancer and female breast cancer were diagnosed in the U.S. Germline mutations in the BRCA1 and BRCA2 genes account for 5-10% of breast cancers and 15% of ovarian cancers.¹⁻³ This translates to 14,000-27,000 high-risk cancer survivors who may be impacted by HBOC. Women with inherited HBOC gene mutations who have had breast cancer are at higher risk of ovarian cancer and a second breast cancer (Figure 1), and possibly other cancers.⁴

Technological advances in DNA sequencing have now made it possible to test multiple genes simultaneously using multiplex gene panels.^{2,5-18}

[figure not shown]

CGRA Personalizes Care and is Recommended for

High-Risk Breast and Ovarian Cancer Survivors. CGRA is an evidence-based strategy that informs medical management options that can improve outcomes.^{14,17,19} CGRA involves genetic counseling +/- genetic testing. There is evidence that CGRA by genetic professionals improves accuracy of risk perceptions, enables informed decision making, personalizes care, and does not cause adverse psychological outcomes.^{14,16,20-22} National

organizations have issued guidelines recommending CGRA for breast and ovarian cancer survivors who may be at risk for HBOC.^{17,20,23,24} CGRA in HBOC survivors impacts public health (Figure 2).^{4,17} If a mutation is identified, testing for the known gene mutation can be offered to relatives to determine if they have the cancer predisposition.^{20,25}

Figure 2. Management of Hereditary Breast and Ovarian Cancer for Survivors

Translation of HBOC Discoveries & Guidelines to Practice Has Been Disappointingly Slow. Genetic counseling, guidelines for referral, and testing for HBOC, have been available for >20 years. However, adoption has been slow. It is estimated that <50% of high-risk cancer patients receive a CGRA referral from their providers, <35% of these women receive genetic counseling and <10% receive testing.^{4,26-33} Many women who receive referrals do not adhere to their provider recommendations.^{28,34-44}

1.3 Research Design and Methods

This is a retrospective cohort study of women diagnosed with aggressive breast or ovarian cancer in New Jersey, New Mexico, and Colorado. This application covers the work being completed in New Jersey only. The NJSCR will identify women recently diagnosed breast and ovarian cancer who meet the following inclusion/exclusion criteria. (Table 1)

We will not include any of the following special populations:

- Adults unable to consent
- Individuals who are not yet adults (infants, children, teenagers)
- Pregnant women
- Prisoners

Table 1: Inclusion / Exclusion Criteria for NJSCR recruitment

Cancer Type	Inclusion	Exclusion
Breast Cancer survivors	Hispanic or non-Hispanic Female 21 years of age or older English or Spanish-speaking Breast cancer history = breast cancer at the age or before age 50 OR triple negative breast cancer at or before age 60 OR two or more primary breast cancers Primary Cancer dx'd prior to breast cancer is OK Primary tumor dx'd after breast cancer is OK	Have had prior genetic counseling or testing for hereditary breast and/or ovarian cancer Unable to give informed consent (incoherent, dementia) No access to a telephone In hospice care Incarcerated Permanent residence outside of NJ Planning on relocating out of NJ within the next year
Ovarian Cancer Survivors	Hispanic or non-Hispanic Female 21 years of age or older English or Spanish-speaking History of ovarian, fallopian, or peritoneal cancer diagnosed at any age Primary Cancer dx'd prior to ovarian cancer is OK Primary tumor dx'd after ovarian cancer is OK	Have had prior genetic counseling or testing for hereditary breast and/or ovarian cancer Unable to give informed consent (incoherent, dementia) No access to a telephone In hospice care Incarcerated Permanent residence outside of NJ Planning on relocating out of NJ within the next year

A. Research procedures:

The NJSCR will conduct patient recruitment following their established Standard Operating Procedures (NJSCR Data Repository #Pro20140000992).

Recently diagnosed cases will be identified by staff at the NJSCR and reviewed by a Certified Tumor Registrar (CTR) for study eligibility (Table 1). We will update address information for the case and the physician of record. Each person will be assigned an arbitrary study ID and imported into the study tracking database “CRIMSoN.” NJSCR staff will send a letter to the patient’s diagnosing physician of record to notify the physician that his/her patient is eligible for participation in the study. Physicians are asked to notify NJSCR if the patient should not be contacted for participation (i.e., deceased). Two weeks after the physician letter is mailed, NJSCR staff will send the eligible patient a packet of study materials, including:

1. An introductory letter containing a brief description of the study (English or Spanish), a statement of how the patient was determined to be eligible for inclusion into the study, a statement of how the patient was identified via the NJSCR, and a request for the patient’s participation;
2. Two copies (one to sign and return, one to keep) of an “agreement to contact” sheet that contains all aspects of informed consent and a location to sign;
3. An information sheet that contains all aspects of HIPAA;
4. An NJSCR Study FAQ brochure which aims to answer common questions about the NJSCR and study participation; and,

5. A postage paid return envelope for the completed Agreement to Contact form.

One week (or five business days) after the initial mailing, staff at the NJSCR will conduct six to eight follow-up phone calls at varying times of the day and different days of the week with at least one evening call made between the hours of 5-8pm and at least one call made on a weekend. Those reached by phone will be given the option to provide a verbal consent to be contacted, which will be recorded in the tracking database. A Spanish-speaking NJSCR staff member will contact individuals who indicated Spanish as a preferred language during patient contact. Additional recruitment packets will be mailed upon patient request or if returned for an incorrect address. NJSCR will track all contact with the patient using the CRIMSON tracking database.

NJSCR contracted with Salt City Research to design a tracking tool for patient contact studies, particularly mail and phone contact, and participant response status. CRIMSON works with SEER*DMS (NJSCR registry database system) and includes modifiable reports and tracking for mode of contact. Key features of CRIMSON include: (1) enhanced report functions and data collection for key recruitment statistics across all studies; (2) enhanced interoperability with SEER*DMS to reduce manual entry of data and improve data sharing; (3) improved data integrity, quality, consistency, and collection through implementation of validation tools and triggers, elimination of data redundancies, and execution of auto-fill and auto-coding of key variables to remove manual entry of data whenever possible; and (4) implementation of relational structure of the data system allowing for all studies and associated administrative data to be housed within a single data system.

After consent / “Agreement to Participate”, NJSCR staff will transfer data securely for consented individuals to the prime site for enrollment and participation in the study.

Briefly, the prime site will randomize the individuals into one of three study arms. NJSCR will not be involved in the intervention. Women will be randomized to one of three study arms: UC, mailed TP, and TCN delivered by a health education specialist. Group assignment will occur at the end of the baseline interview using a computerized randomized list. The interventions will take place ideally within 2 weeks but no more than 30 days upon completion of the baseline survey. Follow-up surveys will be conducted 1 month (to assess mediation), 6 months, and 12 months after randomization for the UC arm, and 1 month, 6 months, and 12 months after the interventions for TP and TCN arms. During the 6 and 12 month surveys, participants will be asked if they'd like to participate in future research. All survey questions will be stored in the REDCap database. The 3 arms will be compared with regard to uptake of CGRA at 6 months (primary outcome) and 12 months, and secondary outcomes including psychosocial and decision-making factors, CGRA preferences, genetic test uptake at 6 and 12 months, and cost outcomes at 6 and 12 months.

B. Recruitment in New Jersey will begin in July 2018 once SRB and IRB approvals are received and continue through July 2020. The tasks include SRB approval, IRB approval, case identification, “Agreement to Contact”, data analysis, and publications.

Overall Study Timeline for the Principal Investigator ([name]) once the person is enrolled:

- The duration of a woman's participation in the study will be approximately 12-13 months depending on study arm.
- The duration estimated for the investigators to complete the study is approximately 5 years and the estimated time needed to complete primary and secondary analyses that address all the study's aims is about 18 months.

Month 1-7: Start-up, refine data collection and intervention materials, database creation, train health education specialists, IRB approvals

Month 8-32: Recruit and conduct baseline surveys

Months 8-32: Intervention implementation

Months 7-43: Intermediate and final outcome assessments, data cleaning

Months 44-60: Data analysis, presentations, reports, manuscript preparation and publications, and submit competitive renewal

1.4 Preliminary Data

Solutions are Needed to Expand Reach and Access, and Reduce HBOC-related Disparities. Psychoeducational interventions that inform, motivate, and address barriers and facilitators to clinical services are typically more effective in facilitating access to recommended health services.^{41,45-49} Evidence shows that patients who are equipped with skills are more likely to follow through with recommended care and have better outcomes at reduced costs.^{50,51}

For our diverse target population, both print and telephone have been found to be acceptable ways to communicate CGRA information but tailored counseling and navigation vs. targeted print has not been effectively tested in this context.^{39,52-54} The purpose of this randomized trial is to test the efficacy compared to usual care in increasing CGRA for HBOC. Cancer registries are in an ideal position to identify and reach large numbers of high-risk cancer survivors who may benefit from risk information that can help them make informed decisions about their health and/or information pertinent to their biological relatives.^{55,56}

Each year NJSCR participates in a variety of research studies to use data collected by the NJSCR. Eligible cases are actively being contacted for 10 patient contact studies and 2 additional patient contact studies are in the start-up phases. All are approved by the SRB and IRB. Over the past three years we successfully completed 7 patient contact studies that resulted in several scientific publications. A complete bibliography of successful NJSCR research can be found on our website:

http://www.state.nj.us/health/ces/documents/njscribliography_seer_1980_2017.pdf

1.5 Sample Size Justification

The overall study will require a sample size of 642 participants, as shown below in Figure 1, CONSORT flow diagram. The 642 (214 per arm) high-risk breast and ovarian cancer survivors will be randomized to one of the 3 study arms. Participants will be recruited from both the NM, NJ, and CO cancer registries. In New Jersey, we will contact 7,000 breast and ovarian cancer survivors to obtain 700 consents, expecting that 50% of identified individuals sampled and screened for eligibility will fall under our exclusion criteria or will be ineligible for other reasons, 25-28% will consent, and we will retain 80% over the course of the study. Table 2 shows the number of cases available for contact from the NJSCR.

Based on our experience recruiting through population-based tumor registries there are no anticipated barriers or challenges that will prevent us from reaching our accrual goal and we believe that enrollment will be feasible. Standard methods are used to estimate contact and response rates¹¹³ and these rates are consistent with other studies that used similar population-based sampling and recruitment strategies for health promotion intervention studies in our region (response rates are typically higher for female survivors).^{54,57,109,114-116} Based on our calculations and considerable experience recruiting individuals from state cancer registries to epidemiologic and

behavioral intervention studies, we are confident that we have a sufficient pool of women who are at increased HBOC risk to recruit into the study. Using data from cancer registries in NJ, NM, and CO, we can estimate the number of potentially eligible living female breast and ovarian cancer survivors who meet the criteria for a referral for CGRA by a credentialed genetic professional.

Table 2: Number of Eligible Women, by cancer type, NJ, annual estimates

[figure not shown]
Cancer Type	NJ Annual* No. of Eligible Cases	% Hispanic
Ovary	269	10
Fallopian Tube	21	<1
Peritoneal	14	<1
Breast Early Onset	1849	18
Breast Triple Negative	425	16
Breast 2+ primaries	1059	10

New Jersey State Cancer Registry October 25, 2016 analytic file. Processed in December 2017.

*Annual averages are based on counts from the five most recent diagnosis years (2011-2015)

Figure 1: Overall Sample Size and Study Design

GRACE Study CONSORT Diagram

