sample size per arm of 182 exceeds the planned final sample size of 164. Randomizing 548 participants based on 1:1:1 relative sizes ensures > 80% power for all contrasts. Assuming up to 20% attrition after baseline assessment, we will recruit 182 individuals for each arm. The sample size and power was evaluated using PASS13 software.¹⁹⁸ A total of 548 individuals will be required (182 per arm x 3 arms). NJSCR will recruit 700 individuals and the remaining sample size will be obtained from other participating registries.

C. Securing the Data

All computers are password protected and in a secure office. The database holding PII is password protected also and is restricted to NJSCR-CSRP research staff. To protect personal identifiers, each woman will be assigned an arbitrary identification number and this will be used for communication between research staff. Any PII that is consented to be released will be transferred in a secure, encrypted manner.

All electronic data are saved on a secure, encrypted server and backed up regularly on a secure server. Paper files are secured in locked file cabinets in the locked office.

At the Prime Site, the Principal Investigator ([name]) will provide each study participant with a Registry Identifier and Participant Identifier. Data will be linked by these two keys. Names and birthdates (and other PHI) that could be used to identify individuals will not be entered into the main study database. These data will be stored in an excel file which will be kept separate from research data. As aforementioned, the biostatisticians who analyze the data will be blinded to participant's study arm.

Data for this study, including PIII, will be stored by NJSCR for 6 years after study completion as required by the Rutgers IRB.

D. Data Quality Control

Quality Control – The CRIMSoN patient tracking database will reviewed regularly to assure quality.

E. Data Handling

At the New Jersey State Cancer Registry, the Site Principal Investigator ([name]) will be responsible for data protection and handling. All data will be stored indefinitely. Only authorized and trained research staff will have access to the data and will be responsible for the transmission of the data. Any PII for consented cases will be shared with the Principal Investigator using Rutgers LiFT, or another large file encryption mechanism.

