Multiple imputation assumed missing at random and was based on verified CGRA within 6months and demographic information; having a primary care provider; cancer site (breast v ovarian cancer); and number of first- and second-degree relatives with cancer, as well as the a priori interaction of the intervention with potential effect modifiers: race, ethnicity, health insurance status, literacy level, and household income. Ten imputed data sets were generated using IVEware with sequential regression, and Rubin's rule was applied to combine results using SAS Proc Mianalyze. Odds ratios, CGRA percentages, and 95% CIs were conducted using SAS v9.4.

With a final sample size of at least 212 per arm and 3% of CGRA for TP or UC, the minimum detectable OR for comparisons between TCN and TP or between TCN and UC is 1.86 with 80% power and 5% overall type I error rate (2.5% for each comparison) after multiplicity adjustment.

Demographic and clinical characteristics of participants were compared among three arms using ANOVA and chi-square analysis. The mediators at baseline and 1 month were compared (within arms and between arms) using paired *t*-tests and two-sample *t*-tests; CGRA uptake at 6 months was compared using a chi-square test.

Generalized structural equation modeling (GSEM) was used for mediation analysis because CGRA uptake is a binary outcome. All 1-month cognitive and emotional mediators were controlled for baseline levels and all scores were standardized. Maximum likelihood estimation was used for estimating regression coefficients/parameters. Indirect effects were estimated, and a bootstrapping method (1,000 replications) was used to construct 95% confidence intervals.

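### The protocol gives two different totals to randomise, 642 (section 1.5) and 548 (section 6.1.B), and at the stated 20% loss neither yields the 182 analysed per arm behind the quoted power.

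*Protocol*

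**What the plan says.** Protocol section 1.5 gives the requirement for the whole study: "The overall study will require a sample size of 642 participants". It then says "The 642 (214 per arm) high-risk breast and ovarian cancer survivors will be randomized to one of the 3 study arms", and it expects 80% retention over the study.

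Section 6.1.B (Power Analysis) gives another total for the same three-arm study: "Randomizing 548 participants based on 1:1:1 relative sizes ensures > 80% power for all contrasts", and "A total of 548 individuals will be required (182 per arm x 3 arms"). It uses 182 in two ways. In one sentence 182 is the number recruited, with attrition already in view: "Assuming up to 20% attrition after baseline assessment, we will recruit 182 individuals for each arm". In another it is the final number: "sample size per arm of 182 exceeds the planned final sample size of 164". Both power statements, 95.7% for UC vs TP and 84.5% for TP vs TCN, are made at 182 per arm.

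On the registries, section 6.1.B says "NJSCR will recruit 700 individuals and the remaining sample size will be obtained from other participating registries". Sections 1.5 and 4.5 describe the same 700 as consents, from 7,000 women contacted.

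The SAP (item 2) works with another figure: "With a final sample size of at least 212 per arm".

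**The concern.** Both sections describe what will be randomised, so the two totals cannot be read as a planned number and a subset of it. Someone running the trial from section 6.1.B would stop 94 women earlier than someone running it from section 1.5.

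The choice affects power. Section 6.1.B attaches its assurance of more than 80% power to 548 randomised, but its power figures are computed at 182 per arm with no allowance for loss. If 182 is the number recruited and up to a fifth are lost, the analysed sample is smaller than the one behind those figures. The comparison most exposed is TP vs TCN, which bears directly on the hypothesis that tailored counselling does better than print.

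**Working it through.** **Inputs.** From section 6.1.B: UC uptake 7%; a 15-point difference for UC vs TP, taken here as 7% vs 22%, at alpha 0.017; 19% vs 34% for TP vs TCN at alpha 0.025; two-sided tests; 182 per arm; up to 20% attrition; 548 in total. From section 1.5: 642 in total, 214 per arm, 80% retained.

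**Formula.** Two-sided comparison of two proportions with pooled variance under the null, n analysed per arm, p̄ the mean of the two rates and Δ their difference:

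power = Φ{[Δ√n − z·√(2p̄(1−p̄))] / √(p₁(1−p₁) + p₂(1−p₂))}

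**Step 1: reproduce the plan's figures at n = 182** (√182 = 13.491, so Δ√n = 0.15 × 13.491 = 2.024).
- UC vs TP: z = 2.387; √(2 × 0.145 × 0.855) = 0.498; √(0.0651 + 0.1716) = 0.487. (2.024 − 1.188)/0.487 = 1.717, power **95.7%**.
- TP vs TCN: z = 2.241; √(2 × 0.265 × 0.735) = 0.624; √(0.1539 + 0.2244) = 0.615. (2.024 − 1.399)/0.615 = 1.016, power **84.5%**.

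Both match the protocol, so its figures assume 182 analysed per arm.

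**Step 2: check the totals.**
- 642 − 548 = 94.
- 3 × 214 = 642, but 3 × 182 = 546, not 548 (a difference of two women, of no consequence for power).
- 642 × 0.80 = 513.6, so 548 is not what remains of 642 at 20% loss.
- 182/214 = 0.850, so 642 gives 182 analysed only at about 15% loss.
- 182/0.80 = 227.5, so analysing 182 per arm at 20% loss needs 228 per arm, 684 in total.

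**Step 3: apply 20% loss to each total.**

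| Randomised | Analysed per arm | UC vs TP | TP vs TCN |
|---|---|---|---|
| 548 | 548 × 0.80/3 ≈ 146 | 90.0% | 74.9% |
| 642 | 642 × 0.80/3 ≈ 171 | 94.4% | 82.0% |
| Protocol's figures | 182 | 95.7% | 84.5% |

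**Step 4: sensitivity to the test.** Section 6.1.B names a likelihood ratio test. Exact enumeration of that test gives 96.6% and 85.1% at 182, 95.5% and 82.5% at 171, and 91.8% and 75.7% at 146. The conclusion is the same. Comparisons should stay within one method; the pooled formula is used here because it reproduces the protocol's figures.

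**The case against.** **The 20% is a ceiling.** Section 6.1.B allows up to 20%, and section 1.5's 80% retention covers the whole study, about 12 to 13 months per woman, whereas the primary outcome is at 6 months. The documents give no 6-month loss. If it were 15% (an assumption), 642 would leave 182 per arm and the quoted powers would hold. This stands: 642 is compatible with the stated power, and even at full attrition it keeps both quoted contrasts above 80%. It does not remove the conflict with 548, and the protocol never states the rate that would make 642 and 182 agree.

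**The power shortfall at 548 depends on reading 182 as recruited.** Also true. But section 6.1.B says so in terms, and ties its power assurance to randomising 548. If 182 is instead the analysed number, the text is wrong in calling 548 the number randomised.

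**New Jersey's 700.** A reader might infer that 700 exceeds either total and so leaves no place for the other two states. The documents do not support that. Sections 1.5 and 4.5 count consents, and section 1.3 places these before transfer to the prime site, the baseline interview and randomisation. Only section 6.1.B's wording, which expects a remainder after the 700, mixes the units.

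**The SAP's 212 per arm.** A reader might take this as proof that 642 was the governing target. It is consistent with 642, and item 5 gives 212 as the size of the TCN arm. But the SAP is dated January 2025, is written largely in the past tense, and calls 212 a final size. It does not establish which planned total governed. It does suggest that enrolment was not stopped at 182 per arm.

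**Conclusion.** The sample-size text is wrong as written. Two sections give totals to randomise that differ by 94 women, and at the stated 20% attrition neither gives the 182 analysed per arm that the quoted power requires. With 548, TP vs TCN power is 74.9%, which contradicts the assurance of more than 80% for all contrasts. With 642, power is 94.4% and 82.0%: adequate for the two quoted contrasts, but 1.3 and 2.5 points below the quoted figures.

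This rests on the protocol's own uptake rates and alpha levels, on 7% vs 22% for UC vs TP, and on the full 20% being lost before the primary analysis. With smaller loss the shortfall shrinks, and for 642 it disappears at about 15%. This is a defect in the stated target and power. It does not show that the trial as run was underpowered.

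**What to change.** 1. Use 642 randomised (214 per arm) in both sections. In section 6.1.B, delete 548 and the 182-by-3 product as the randomised total.
2. State one attrition rate to the primary outcome and the analysed number it gives, in both sections. Either 20% loss, 171 analysed per arm and power of about 94% and 82% by the method behind the current figures; or 15% loss, 182 analysed per arm and power of 95.7% and 84.5%.
3. Use 182, if it is kept, only for the number analysed.
4. In section 6.1.B, label New Jersey's 700 as consents (agreements to contact) obtained before randomisation, as section 1.5 does, and remove the wording that sets it against the randomised total.

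The cost is protocol wording. If 20% loss is kept, the quoted power falls by about 1 to 2.5 points. No patients are needed beyond the 642 already in section 1.5.
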